7.4.1.6. Regulatory Reporting Requirements for SAEs

Prompt notification by the investigator to GSK of SAEs related to study treatment (even for non- interventional post-marketing studies) is essential so that legal obligations and ethical responsibilities towards the safety of subjects and the safety of a product under clinical investigation are met.

GSK has a legal responsibility to notify both the local regulatory authority and other regulatory agencies about the safety of a product under clinical investigation. GSK will comply with country specific regulatory requirements relating to safety reporting to the regulatory authority, Institutional Review Board (IRB)/Independent Ethics Committee (IEC) and investigators.

Investigator safety reports are prepared for suspected unexpected serious adverse reactions according to local regulatory requirements and GSK policy and are forwarded to investigators as necessary.

An investigator who receives an investigator safety report describing a SAE(s) or other specific safety information (e.g., summary or listing of SAEs) from GSK will file it with the IB and will notify the IRB/IEC, if appropriate according to local requirements.

7.4.2. Pregnancy

- Details of all pregnancies in female subjects and female partners of male subjects will be collected after the start of dosing and until the follow-up visit.
- If a pregnancy is reported then the investigator should inform GSK within 2 weeks of learning of the pregnancy and should follow the procedures outlined in [Appendix 3](#).

7.4.3. Physical Exams

- A complete physical examination will include, at a minimum, assessment of the Cardiovascular, Respiratory, Gastrointestinal and Neurological systems. Height and weight will also be measured and recorded.
- Investigators should pay special attention to clinical signs related to previous serious illnesses

7.4.4. Vital Signs

- Vital signs will be measured in semi-supine position after 5 minutes rest and will include temperature, systolic and diastolic blood pressure (BP) and pulse rate.

7.4.5. Clinical Safety Laboratory Assessments

All protocol required laboratory assessments as detailed in [Table 1](#) must be conducted in accordance with the Laboratory Manual, and Protocol Time and Events Schedule. Laboratory requisition forms must be completed and samples must be clearly labelled with the subject number, protocol number, site/centre number, and visit date. Reference ranges for all safety parameters will be provided to the site by the laboratory responsible for the assessments.

If additional non-protocol specified laboratory assessments are performed at the institution's local laboratory and result in a change in subject management or are considered clinically significant by the investigator (e.g., SAE or AE or dose modification) the results must be recorded in the CRF.

Parameters to be tested are listed in [Table 1](#).

Table 1 Protocol Required Safety Laboratory Assessments

| Laboratory Assessments | Parameters |
|--|---|
| Other Screening Tests | 
 • FSH and estradiol (as needed in women of non-child bearing potential only) • Urine hCG Pregnancy test (as needed for women of child bearing potential)¹ |
| 
NOTES :
 
1. Local urine testing will be standard for the protocol unless serum testing is required by local regulation or ethics committee.
 | |

7.5. Biomarker(s)/Pharmacodynamic Markers

7.5.1. Exploratory Biomarkers

With the subject's consent, blood samples will be collected during this study and used for the purposes of measuring exploratory biomarkers, including but not limited to, blood eosinophil and serum periostin levels on Day 1 pre-dose (baseline) and following inhaled administration of FF/VI.

Samples will be collected at the time-points indicated in the Time and Events Table in Section 7.1. The timing of the collections may be adjusted on the basis of emerging data from this study or other new information in order to ensure optimal evaluation of the PD endpoints. Analyses of these biomarker data may be reported separately. Further details will be provided in the SRM.

8. DATA MANAGEMENT

- For this study, subject data will be entered into GSK defined CRFs, transmitted electronically to GSK or designee and combined with data provided from other sources in a validated data system.
- Subject paper diaries will also be used for when the subjects are at home, for collection of dosing information, details of any AEs/SAEs and concomitant medications. These will then be transcribed into the CRF by clinic staff.
- Management of clinical data will be performed in accordance with applicable GSK standards and data cleaning procedures to ensure the integrity of the data, e.g., removing errors and inconsistencies in the data.
- Adverse events and concomitant medications terms will be coded using MedDRA (Medical Dictionary for Regulatory Activities) and an internal validated medication dictionary, GSKDrug.
- CRFs (including queries and audit trails) will be retained by GSK, and copies will be sent to the investigator to maintain as the investigator copy. Subject initials will not be collected or transmitted to GSK according to GSK policy.

9. STATISTICAL CONSIDERATIONS AND DATA ANALYSES

9.1. Hypotheses

No formal hypothesis will be tested, an estimation approach will be adopted to address the primary objective. A point estimate and corresponding 95% CI will be constructed for the treatment ratio of test treatment, $\mu(\text{test})$ and reference treatment(reference), where FF/VI 100/25mcg is the test treatment and placebo the reference treatment.

9.2. Sample Size Considerations

9.2.1. Sample Size Assumptions

Approximately 28 subjects will be recruited to ensure 24 evaluable subjects. An evaluable subject is defined as a subject who completes dosing and critical assessments in both treatment periods.

A re-analysis of FeNO data from the FFA10028 study [GlaxoSmithKline Document Number [GM2003/00418/00](#)] was carried out to estimate the within-subject coefficient of variation (CVw) from a repeated measures analysis using the treatments and time-points most relevant to this study (i.e. FF and placebo treatments and all pre-dose, 12 hour and 24 hour time-points on all days assessed (Days 1-5)). A mixed effects repeated measures model was fitted with fixed effect terms for period, treatment, day, time, period-level baseline, subject-level baseline, (period-level baseline)*day*time interaction term and the treatment*day*time interaction term. Day*time interaction term was fitted as a repeated measure. FeNO was loge-transformed prior to deriving subject-level baseline and period-level baseline. The CVw from the re-analysis was 21.6%.

Based upon a CVw of 21.6% and a sample size of 24 subjects, it is estimated that the lower and upper bounds of the 95% confidence interval for the treatment ratio (FF/VI vs Placebo) for FeNO will be approximately 14% of the point estimate.

9.2.2. Sample Size Sensitivity

A sensitivity analysis was conducted in the event that the variability deviates from that estimated from the FFA10028 study [GlaxoSmithKline Document Number [GM2003/00418/00](#)]. The table below shows precision estimates for varying within subject coefficient of variability keeping all other variables constant.

| Confidence Level | Sample Size (N) | CVw% | Half Width (%) |
|------------------|-----------------|------|----------------|
| 0.95 | 24 | 15% | 10% |
| | | 20% | 13% |
| | | 25% | 16% |
| | | 30% | 20% |

The precision estimates are deemed acceptable to assess the study objectives.

9.2.3. Sample Size Re-estimation or Adjustment

No sample size re-estimation or adjustment will be performed.

9.3. Data Analysis Considerations

9.3.1. Analysis Populations

Statistical analyses of the pharmacodynamic parameter data will be the responsibility of Clinical Statistics, GlaxoSmithKline.

Subjects excluded from any analyses will be fully documented and justified within the clinical study report. All analyses will be based on the actual treatment that each subject received. Any departures from the planned treatment according to the randomisation schedule will be documented in the clinical study report.

The 'All Subjects' population will consist of all subjects randomised to treatment who received at least one dose of study treatment.

The 'Pharmacodynamic' (PD) population will consist of all subjects from the 'All Subjects' population who had at least one PD assessment.

9.3.2. Interim Analysis

No interim analysis is planned.

9.4. Key Elements of Analysis Plan

9.4.1. Primary Analyses

Following \log_e -transformation, primary endpoint of FeNO change from baseline ratio following cessation of treatment will be analyzed using a mixed effects repeated measures model with fixed effect terms for period, treatment, day, time, (period-level baseline)*day*time interaction term, treatment*day*time interaction term, period-level baseline and subject-level baseline. Day*time interaction term will be fitted as repeated measure. FeNO will be \log_e -transformed prior to deriving subject-level baseline and period-level baseline. Point estimates and their associated 95% confidence intervals will be constructed for the difference [FF/VI 100/25mcg] – [Placebo] at each timepoint (AM/PM i.e. pre-dose & 12 hours) on each day. The point estimates and their associated 95% confidence intervals will then be back-transformed to provide point estimates and 95% confidence intervals for the ratios, [FF/VI 100/25mcg]/[Placebo] for each day and AM/PM timepoint. Further details will be provided in the Reporting and Analysis Plan (RAP) regarding the model to be fitted and model checking.

9.4.2. Secondary Analyses

Secondary endpoints of FeNO change from baseline ratio during treatment and FEV₁ will be analysed similarly to the primary FeNO endpoint. FEV₁ will not be log-transformed.

PEF data will be listed and summarised.

Further details will be provided in the RAP.

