3. OBJECTIVE(S) AND ENDPOINT(S)

| Objectives | Endpoints |
|--|--|
| Primary | |
| 
 To characterise the fraction of exhaled nitric oxide (FeNO) time profile following repeat administration of fluticasone furoate/vilanterol (FF/VI) 100/25mcg combination in comparison with placebo in subjects with asthma. | 
 Change from baseline FeNO over time following the cessation of repeat dose treatment with FF/VI. |
| Secondary | |
| 
 Change in FeNO over the treatment period following repeat administration of FF/VI 100/25mcg combination in comparison with placebo in subjects with asthma. To determine the Peak Expiratory Flow (PEF) during and following repeat administration of FF/VI 100/25mcg combination in comparison with placebo in subjects with asthma. To determine FEV₁ following repeat administration of FF/VI 100/25mcg combination in comparison with placebo in subjects with asthma | 
 Change from baseline FeNO over the FF/VI treatment period. Measurement of PEF during treatment and following cessation of repeat dose treatment with FF/VI. Measurement of FEV₁ pre-treatment and for up to 7 days after cessation of repeat dose treatment with FF/VI. |
| Exploratory | |
| 
 To investigate the effect of repeat administration of FF/VI 100/25mcg combination on exploratory biomarkers, including but not limited to, blood eosinophil levels and serum periostin levels, in comparison with placebo in subjects with asthma. | 
 Measurement of exploratory biomarkers, including but not limited to, blood eosinophil and serum periostin levels at baseline, and at various time points after cessation of repeat dose treatment with FF/VI. |

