Primary Analyses	
FeNO, change from baseline ratio will be formally analysed following log_e-transformation. A mixed effects repeated measures model will be fitted with fixed effect terms for period, treatment, day, time, (period-level baseline)*day*time interaction term, treatment*day*time interaction term, period-level baseline and subject-level baseline. Day*time interaction term will be fitted as repeated measure. FeNO will be log_e-transformed prior to deriving subject-level baseline and period-level baseline.

Overview	Key Elements of the RAP
Secondary Analyses	FeNO change from baseline ratio during treatment and FEV1 will be analysed similarly to the primary FeNO endpoint. FEV1 will not be log-transformed prior to analysis. PEF will be summarised.
Safety Analyses	Safety data will be summarized
Biomarker Analyses	Exploratory endpoints of biomarkers will be summarized

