2. SUMMARY OF KEY PROTOCOL INFORMATION

2.1. Changes to the Protocol Defined Statistical Analysis Plan

There were no changes or deviations to the originally planned statistical analysis specified in the protocol [Dated: 12-JAN-2016].

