8. SECONDARY STATISTICAL ANALYSES

8.1. Pharmacodynamic Analyses

8.1.1. Overview of Planned Pharmacodynamic Analyses

The secondary Pharmacodynamic analyses will be based on the “Pharmacodynamic (PD)” population, unless otherwise specified.

[Table 4](#) provides an overview of the planned Pharmacodynamic analyses, with further details of data displays being presented in [Appendix 10](#): List of Data Displays.

Table 4 Overview of Planned Pharmacodynamic Analyses

Endpoint	Absolute				Change from Baseline							
	Summary		Individual		Stats Analysis			Summary		Individual		
	T	F	F	L	T	F	L	T	F	F	L	
FeNO ^[1]					Y	Y	Y					
FEV1	Y			Y	Y	Y	Y	Y				
PEF	Y			Y								

NOTES:

[1] FeNO will be \log_e transformed prior to analysis.

- T = Table, F = Figures, L = Listings, Y = Yes display generated.
- Summary = Represents TF related to any summaries (descriptive statistics) of the observed raw data.
Individual = Represents FL related to any displays of individual subject observed raw data.

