11.10.5. Pharmacodynamic Tables

Efficacy: Tables					
No.	Population	Example Shell	Title	Programming Notes	Deliverable [Priority]
Pharmacodynamic Parameters					
2.1.	PD	LB1	Summary of Exhaled Nitric Oxide Data	Parameter with units, both untransformed and transformed	Headline [1] SAC [2]
2.2.	PD	LB1	Summary of Change from Baseline Exhaled Nitric Oxide Data	Parameter with units for untransformed data	SAC [2]
2.3.	PD	LB1	Summary of Ratio from Baseline Exhaled Nitric Oxide Data	Parameter with units for transformed data	Headline [1] SAC [2]
2.4.	PD	PD_T1	Summary of Repeated Measures Statistical Analysis of Ratio from Baseline Exhaled Nitric Oxide Data after cessation of repeat dose of treatment		Headline [1] SAC [2]
2.5.	PD	PD_T1	Summary of Repeated Measures Statistical Analysis of Ratio from Baseline Exhaled Nitric Oxide Data		SAC [2]
2.6.	PD	LB1	Summary of Spirometry data		SAC [2]
2.7.	PD	LB1	Summary of Change from Baseline in Spirometry data		SAC [2]
2.8.	PD	PD_T1	Summary of Repeated Measures Statistical Analysis of Change from Baseline FEV1 Data		SAC [2]

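### The PEF secondary objective is a comparison with placebo, but the plan gives PEF no within-subject FF/VI–placebo contrast and no confidence interval

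*Protocol*

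**What the plan says.** Protocol section 3 sets the objective: "To determine the Peak Expiratory Flow (PEF) during and following repeat administration of FF/VI 100/25mcg combination in comparison with placebo in subjects with asthma". The matching endpoint is "Measurement of PEF during treatment and following cessation of repeat dose treatment with FF/VI". SAP 2.2 repeats both.

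Protocol 9.4.2 separates the secondary endpoints. For two of them, "Secondary endpoints of FeNO change from baseline ratio during treatment and FEV₁ will be analysed similarly to the primary FeNO endpoint". For the third, "PEF data will be listed and summarised". The SAP synopsis agrees ("PEF will be summarised"), and SAP 2.1 confirms that nothing was added: "There were no changes or deviations to the originally planned statistical analysis specified in the protocol".

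In SAP Table 4 ("Overview of Planned Pharmacodynamic Analyses"), the PEF row is marked for a summary table of absolute values and an individual listing. It is blank under statistical analysis and under change from baseline. SAP 8.1.2 specifies models for FeNO during treatment and for FEV1 only.

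SAP 11.5.2.1 does define a PEF baseline, the Day 1 pre-dose value in each period. In SAP Appendix 10 no table, figure or listing has PEF in its title. The nearest titles are Tables 2.6 and 2.7 (the latter is "Summary of Change from Baseline in Spirometry data") and Listing 21, all of which refer to spirometry.

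**The concern.** The study is declared to be one of estimation: no hypothesis is tested, and treatment effects are to be reported as point estimates with 95% intervals. In such a study, a comparative objective is met by an estimated contrast and its interval. PEF has neither.

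FEV1 cannot stand in for it. Under Protocol 7.1, FEV1 within a treatment period is scheduled on Day 1, Days 14 to 19, Day 21 and Day 35. PEF is the only lung-function measure scheduled on Days 2 to 13, so the part of the objective that concerns the dosing period rests largely on PEF. About 70 morning and evening readings per period would be collected without a planned comparison.

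The design also matters. Protocol 4.4 prefers a crossover because it needs fewer subjects, and that advantage comes from each subject acting as his or her own control. Separate means and standard deviations by treatment do not carry that information. A reader judging the difference from the two printed SDs would be using between-subject spread.

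**Working it through.** **1. PEF set beside FEV1**

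| Item | FEV1 | PEF |
|---|---|---|
| Objective | determine, in comparison with placebo | determine, in comparison with placebo |
| Endpoint | a measurement, no contrast defined | a measurement, no contrast defined |
| Period baseline in SAP 11.5.2.1 | Day 1 pre-dose | Day 1 pre-dose |
| Change from baseline in SAP Table 4 | yes | no |
| Statistical analysis in SAP Table 4 | yes | no |
| Model in SAP 8.1.2 | yes, FF/VI minus placebo with 95% CI | none |
| Named model table in Appendix 10 | Table 2.8 | none |

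The objective and endpoint wording therefore does not explain the different treatment, and neither document gives a reason.

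**2. The plan's own precision figure (FeNO), to fix the formula**

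Inputs from Protocol 9.2.1: N = 24, CVw = 21.6%. For a two-period crossover I take 22 degrees of freedom.

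- σw = √ln(1 + 0.216²) = 0.2135
- half-width on the log scale = t(0.975, 22) × σw × √(2/24) = 0.5987 × 0.2135 = 0.1278
- upper bound relative to the estimate = exp(0.1278) − 1 = 13.6%

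The protocol states approximately 14%. For CVw of 15, 20, 25 and 30% the same formula gives 9.3, 12.6, 15.9 and 19.2%. Rounded up, these are the 10, 13, 16 and 20% in Protocol 9.2.2. The formula reproduces the plan's figures.

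**3. The same formula for PEF, untransformed, one timepoint or one summary measure**

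Half-width = t(0.975, 22) × √(2/24) × SDw = 0.60 × SDw. The documents give no SDw for PEF, so these values are assumptions:

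| Assumed SDw (L/min) | 20 | 30 | 40 | 50 | 60 |
|---|---|---|---|---|---|
| 95% half-width (L/min) | 12.0 | 18.0 | 23.9 | 29.9 | 35.9 |

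**4. What ignoring the pairing does**

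Let ρ be the correlation between a subject's two periods. At the same t quantile, the unpaired half-width exceeds the paired one by a factor 1/√(1 − ρ). For assumed ρ of 0.5, 0.7, 0.8 and 0.9 this is 1.41, 1.83, 2.24 and 3.16. The plan does not propose an unpaired interval; the factor only shows what two separate summaries leave out.

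**5. Whether the FEV1 model can be carried over unchanged**

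SAP Appendix 8 specifies an unstructured covariance over day-by-time.

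- FEV1: Days 14 to 19 twice daily (12), plus Days 21 and 35, gives about 14 timepoints and 14 × 15/2 = 105 covariance parameters.
- PEF: 35 days × 2 = 70, less the Day 1 morning baseline, gives about 69 timepoints and 69 × 70/2 = 2,415 covariance parameters.

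Twenty-four completers supply 24 × 2 = 48 subject-period profiles. An unstructured matrix over all PEF timepoints cannot be estimated from these.

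**The case against.** The strongest reply is that descriptive PEF was a deliberate choice. It is stated consistently in the protocol synopsis, Protocol 9.4.2, the SAP synopsis and SAP Table 4. The exploratory biomarker objective also refers to comparison with placebo, and it too is only summarised, so the phrase does not always bring a model with it. PEF also serves to monitor asthma stability. All of this is fair, and it shows that the SAP follows the protocol here. It does not explain why a secondary objective is handled like an exploratory one while its twin, FEV1, is modelled.

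Three stronger readings are tempting and are not supported.

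- *The trial will say nothing about PEF against placebo.* A reader might infer this, but a summary by treatment is planned. In a complete crossover with equal sequences, the difference between the two treatment means equals the within-subject point estimate. What is missing is the planned contrast and its interval. The equality also weakens with withdrawals, because SAP 11.7.1 keeps all available data in the summaries.
- *PEF has been dropped from the displays.* Table 4 promises a PEF summary and listing, and SAP section 4 lists PEF among the endpoints of the PD population. The spirometry titles may be meant to cover FEV1 and PEF together: Appendix 10 has no separately named descriptive FEV1 table either, and it writes FEV1 where only FEV1 is meant. Against that, Protocol 7.3.2 and 7.3.3 treat spirometry and PEF as separate assessments, and no programming note settles the matter. The position is unclear; omission is not shown.
- *The FEV1 model need only be rerun on PEF.* The parameter count above rules this out. CSH or CS is available in Appendix 8, but only after unstructured has failed to converge.

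**Conclusion.** The concern stands as a gap in the planned analysis. A comparative secondary objective has no planned within-subject FF/VI–placebo contrast and no 95% CI, while an objective and endpoint in the same words (FEV1) have both. Nothing in the primary analysis or the sample size is affected.

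The gap itself follows from the documents alone. Its size in L/min does not: the 0.60 multiplier rests on 24 completers and 22 degrees of freedom, and the half-widths of 12 to 36 L/min rest on an assumed within-subject SD of 20 to 60 L/min. The gain from pairing likewise depends on an assumed correlation. I rate this as a cheap improvement.

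**What to change.** Before unblinding:

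1. In SAP 8.1.2, add a within-subject analysis of untransformed PEF change from the Day 1 pre-dose baseline in SAP 11.5.2.1, with terms for period, treatment, period-level baseline and subject-level baseline. Extend to PEF the period-level and subject-level derivations, which that section now gives for FeNO and FEV1 only.
2. Apply it to a small pre-specified set of summaries, for example mean morning and mean evening PEF over the on-treatment days and over defined post-treatment windows. Alternatively, keep the individual timepoints and name a parsimonious covariance structure in advance.
3. Report FF/VI minus placebo with a 95% CI for each.
4. In Appendix 10, add the PEF model table. State by title or programming note which display carries the PEF summary and listing promised in Table 4.

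If the sponsor prefers PEF to stay descriptive, the lesser alternative is to reword the objective accordingly, which touches the protocol, and still carry out the clarification of the PEF summary and listing in step 4.

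The cost is SAP text, some programming and a few extra displays, plus choosing the windows or covariance structure in advance. No new data are needed and the sample size does not change.

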9.4.3. Other Analyses

Safety data will be listed and summarised. Exploratory biomarker data (including blood eosinophil and serum periostin data) will be summarized descriptively, if available.

